In addition, we will also collaborate with another study, the Clinic Registry Project (IRB#20160911), which serves as a consent to contact database, to contact eligible participants. They will provide us with contact information for participants in their study who have consented to be contacted by other studies. When contacting participants, the CHW will follow the phone script for calling UHealth consent to contact participants that has been tailored to this study.

8) **Procedures Involved***

Participants will be assessed at three time points (before starting the study, 4, and 7 months after the first interview) on measures of cardiometabolic risk factors (waist circumference, dyslipidemia, hypertension, and glucose), psychosocial functioning, and health-related quality of life.

All participants will read and sign an informed consent document and a HIPAA Research Authorization – Form B approved by the University of Miami Institutional Review Board (IRB). They will initially be provided with a verbal summary of the study and for those who appear to have problems reading the consent form it will be read aloud. Participant payments will be graduated. Participants will receive \$15 on the first visit, \$25 on the second visit, and \$35 on the third visit (total of honoraria = \$75).

Prior to starting the baseline assessments, blood draws will take place at the UM/JMMC Adult HIV Outpatient Clinic. Study staff will obtain initial HDL-C, LDL-C, triglycerides, insulin, and HbA1c levels via review of the electronic medical records. Trained and certified research assistants (RAs) who have at least a bachelor's degree will conduct all assessments in private offices at the UM/JMMC Adult Outpatient HIV Clinic, at a private interview room at the CTRS located on the 7th floor of the Don Soffer Clinical Research Center, or the participant's home. To ensure privacy in the home, we will conduct the interview in a private room with a door of the participant's choosing away from any common areas. In the event that there are other people in the house, the door can be closed to maintain privacy. In the event that an in-person interview is not feasible then the interview will be

IRB Study Number: 20181032

Version 8, Date: 07/16/2021

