conducted over the telephone. At 4 and 7 months after the initial interview, fasting blood samples will be drawn via venipuncture and stored at 4°C until analysis. HOMA will be calculated, providing a measure of insulin resistance. Study measures will be administered after the blood draws.

Assessment Measures

Cardiometabolic Risk: list of current medications, waist circumference, total cholesterol, HDL-C, LDL-C, triglycerides, blood pressure, and HbA1c, will be used to measure cardiometabolic risk.

Dementia Screen: The Mini Mental Status Exam (MMSE) will be used to screen for dementia. A Mungas-adjusted score of 23 or below indicates cognitive impairment.

Walking Ability: The 10 meter walk test will be used to evaluate walking ability, which has been used as a screening instrument to measure functional mobility and gait speed in physical activity interventions with older adults.

Demographics: The CLaRO Demographics Form will be used to collect demographic information (e.g., gender, education, income, preferred language, country of origin, time in the US, etc.) and will include a list of all diagnosed medical conditions and medications.

Acculturation: The 24-item Bidimensional Acculturation Scale (BAS) will be used to measure acculturation.

Depression Severity: The 20-item Center for Epidemiologic Studies Depression (CES-D) Scale and the 9-item Patient Health Questionnaire (PHQ-9) will be used to measure depression severity.

Anxiety Severity: The 7-item Generalized Anxiety Disorder (GAD-7) scale and the 14-item Perceived Stress Scale will be used to measure anxiety severity.

Social Support: Perceived social support will be measured using the 12-item Multidimensional Scale of Perceived Social Support (MSPSS).

Health Related Quality of Life: The SF-12 will be used to assess for health related quality of life.

Physical Activity: The 16-item Global Physical Activity Questionnaire (GPAQ) will be used to measure physical activity.

Stigma: The HIV Stigma Scale (HSS) is a 40 item measure of stigma and psychosocial aspects of having HIV.

IRB Study Number: 20181032

Version 8, Date: 07/16/2021

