Project Evaluation: we will use a project evaluation questionnaire developed by investigators at the CNSA and used in previous studies. The items are a mix of rating scales, yes/no questions, and open-ended questions that allow participants to give feedback in short answer format with specific interest in understanding the participants' opinions regarding the specific components of the intervention.

After the baseline assessment, participants will be enrolled into the HOLA intervention.

Intervention Description: Content and Structure of HOLA

HOLA is a 16-week multi-component, health promotion intervention for older Latinos with subthreshold depression or anxiety. Aside from the maintenance phase (described below), the length and content of the intervention remain unchanged from the pilot study.

The first component of HOLA consists of two manualized social and physical activation sessions. Prior to beginning the group walk phase, each participant will meet individually with a CHW for the physical and social activation session. This session will last 30 minutes. The purpose of this session is to (a) educate potential participants about the goals of the intervention; (b) to motivate participants to engage in physical activity; (c) to increase participants' social activities (d) identify potential obstacles that may interfere with meeting the demands of the intervention; and (e) to brainstorm ways to overcome these obstacles. Participants will meet individually with the CHW for 30 minutes during week 8 to discuss progress of physical and social activity goals. These meetings will be held in the participants' homes.

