Data will be collected using an Apple ipad with pre-programmed questionnaires. Data will be exported to SPSS for analysis. All electronic data will be stripped of identifiers and will be stored in password-protected files. For each data file, a code number will be assigned, and the master list, linking code numbers with names, will be stored separately. The data will be stored on password protected, network computer hard drives at the CNSA, which will only be accessible to the PI.

Blood samples will be stored at the University of Miami Center for AIDS Research Laboratory Sciences Core (D) at -80 °C until analysis. The labels on the blood

IRB Study Number: 20181032

Version 8, Date: 07/16/2021

sample tubes will not contain *participant ID numbers*. The blood samples will be stored in locked freezers in locked rooms within access-limited sections of the building.

All the data will be stored and secured using the procedure implemented by the Data Manager of the CNSA. The access to records and participants data will be allowed only to the study personnel.

Study data request goes through a web-based check-in and check-out procedure implemented by the CNSA. The Data Manager of the Center or designee monitors the logs. Upon de granting of the approval, the requester will either get the hard copy of the data or link to access the electronic data. All the data will not contain any identifying information.

Other parties interested in utilizing the samples for research will be required to provide a written protocol to the PI and the gatekeeper(s) for approval. Should samples be shared, no identifying information will be provided. Material Transfer Agreement will be negotiated between UM and the investigators requesting the data.

10) **Data Management***

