Protection of Risks During Venipuncture: Blood draws will be performed by certified phlebotomists who routinely perform venipuncture; steps will be taken to diminish the risk of minimal discomfort, bruising, excessive bleeding, clotting, and/or fainting. If subjects have unusual symptoms,

IRB Study Number: 20181032

Version 8, Date: 07/16/2021

pain, or any other problems arising due to venipuncture, they can also contact the CHW or PI directly.

14) Potential Benefits to Subjects*

The potential benefits of the project to the participant is that the participant may acquire and practice health behaviors that lead to a decreased risk of developing cardiometabolic disease. The benefit to society is that the project may help demonstrate the effectiveness of the HOLA health promotion intervention in preventing cardiometabolic disease in HIV-infected patients.

In relation to the anticipated benefits, the risks to the subjects are reasonable in relation to the benefit of not developing a life-threatening cardiometabolic disease. Participants are de-identified to minimize loss of confidentiality; suicidality or severe depressed can be addressed by trained mental health professionals; discomfort during venipuncture is mitigated by trained phlebotomists.

15) Vulnerable Populations*

N/A

16) Multi-Site Research*

This is not a multi-site study.

17) Community-Based Participatory Research*

N/A

18) Sharing of Results with Subjects*

Study results will be published in scientific journals. Individual subject results will not be shared unless the safety of the participant is at risk.

19) Setting

Group walks will be conducted at a public park that is centrally located to the participants. All assessments and blood draws will be conducted in private rooms at the at the UM/JMMC Adult HIV Outpatient Clinic.

20) Resources Available

Department of Psychiatry and Behavioral Sciences

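### Baseline laboratory values come from the medical record and follow-up values from stored study samples, with no common laboratory or method stated, so any offset between the two could not be told apart from change over time

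*Combined protocol and SAP*

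**What the plan says.** Section 8 (Procedures Involved) has two consecutive sentences on baseline blood. The first is "Prior to starting the baseline assessments, blood draws will take place at the UM/JMMC Adult HIV Outpatient Clinic". The second is "Study staff will obtain initial HDL-C, LDL-C, triglycerides, insulin, and HbA1c levels via review of the electronic medical records". Neither states a fasting requirement, how old a record value may be, or who runs the assay.

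For follow-up, the same section says "At 4 and 7 months after the initial interview, fasting blood samples will be drawn via venipuncture and stored at 4°C until analysis".

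Section 9 (Data and Specimen Banking) places blood samples at the "Center for AIDS Research Laboratory Sciences Core (D) at -80 °C until analysis". It does not say which visits it covers or that the core performs the assays. Its storage temperature differs from the one in section 8.

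Section 19 (Setting) says "All assessments and blood draws will be conducted in private rooms at the at the UM/JMMC Adult HIV Outpatient Clinic". That fixes where blood is drawn, not where it is measured.

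There is one arm: "After the baseline assessment, participants will be enrolled into the HOLA intervention". Section 10 speaks of randomized subjects when it defines retention, but no second arm is described. Under Aim 3, section 10 uses ANOVA to describe change from baseline to post-intervention. The covariates are age, socioeconomic status, education and medication changes. None of them codes the source of the laboratory value.

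**The concern.** The plan itself prescribes two sources for the same analytes, and the switch falls exactly between baseline and the first follow-up. With no control arm, the laboratory part of Aim 3 rests on within-person change across that switch. A constant difference between the two sources would look like an intervention effect, or hide one. It would carry into planning of the larger trial, which is the purpose of this pilot. Recruiting more men or adding the planned covariates would not remove it.

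**Working it through.** The plan gives no power, alpha, effect size or standard deviation for these outcomes, so it has no figure to reproduce. The check is whether an offset could be separated from change, and what one would do.

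**1. The sources, visit by visit**

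| | Baseline | Month 4 | Month 7 |
|---|---|---|---|
| Source of value | Medical-record review | Study sample | Study sample |
| Fasting stated | No | Yes | Yes |
| Stored until analysis | Not stated for this visit | Yes | Yes |
| Assay laboratory and method | Not named | Not named | Not named |

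**2. Can an offset be separated from change?** Write the value for man *i* at visit *j* as

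Y_ij = a_i + τ_j + δ·S_j + error,

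where τ is zero at baseline, S is 0 at baseline and 1 at months 4 and 7, and δ is the offset, if there is one. The expected contrasts are:

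- month 4 minus baseline: τ4 + δ
- month 7 minus baseline: τ7 + δ
- month 7 minus month 4: τ7 − τ4, free of δ only if both visits use the same method

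With 18 men (section 6) the design matrix has 18 participant columns, 2 visit columns and 1 source column, 21 in all. The source column is the sum of the two visit columns, so the rank is 20. The offset and the change from baseline cannot be estimated separately. If each baseline sample were also assayed by the follow-up method, the rank would be 21 of 21. If all visits used one method with the same handling, the source term would disappear.

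**3. Size on the measurement scale (assumed, not from the documents).** Take an LDL-C of 120 mg/dL and an offset of 3% to 5%:

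- 120 × 0.03 = 3.6 mg/dL
- 120 × 0.05 = 6.0 mg/dL

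The mean change shifts by the full amount, because averaging shrinks random error but not a shift common to all men.

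**4. Effect on a nominal test (assumed: true change zero, paired t-test, two-sided alpha 0.05).** Let d be the offset in standard deviations of the within-person change. The noncentrality is d·√n. Section 10's retention threshold gives 0.85 × 18 = 15.3, so at least 16 completers.

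| d | n = 18 | n = 16 |
|---|---|---|
| 0 | 5% | 5% |
| 0.25 | 17.0% | 15.5% |
| 0.5 | 51.6% | 46.5% |

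These are chances of a nominally significant change caused by the offset alone. The plan sets no alpha, so they show sensitivity only and are not a forecast.

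**The case against.** A reader might infer that baseline values are routine-care results, that follow-up values are measured in the research core, and that the measurement system therefore certainly changes after baseline. The documents do not support that. Section 8 puts clinic blood draws just before the record review, so the record may hold the result of that very draw. Section 9 names the core for storage only, gives no visits, and could cover the baseline sample too. The follow-up samples may go to the same clinical laboratory. In that case the method offset is zero and only a stored-versus-fresh difference could remain. Silence cannot be read as a different laboratory, nor as the same method at months 4 and 7.

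It is also fair that the sizes above are assumptions and that Aim 3 is exploratory in a study not powered to test a hypothesis. Without a control arm, change could not be attributed to HOLA in any case.

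All of this stands as a limit on the point. It does not remove it. The different sourcing is written into the plan, nothing ties the sources together, and an unbridged offset cannot be recovered at analysis.

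**Conclusion.** The point holds in conditional form. The plan sources baseline and follow-up laboratory values differently and neither fixes a common laboratory and method nor bridges them. If laboratory, method or handling differs, the offset is fully confounded with both changes from baseline. The existence and size of an offset are unknown. The 3.6-6.0 mg/dL figure rests entirely on the assumed LDL-C and the assumed percentage.

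The reach is narrow: HDL-C, LDL-C, triglycerides, insulin and HbA1c, and insulin resistance derived from insulin, within exploratory Aim 3. A reader might infer that the primary aim is compromised. It is not, because none of the recruitment, retention and acceptability criteria in section 10 uses a laboratory value. Settling a single baseline fasting rule and storage temperature would help, but would not by itself secure a common laboratory and method. The change is worth making because it is cheap and the bias, if present, cannot be repaired later.

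**What to change.** In section 8, state that the draw already planned before the baseline assessments and the 4- and 7-month draws are collected and handled under the same conditions. State also that they are assayed promptly by one named laboratory with one method per analyte. The clinical laboratory that reports the baseline values is the natural choice. Use a medical-record value as baseline only if it comes from that draw, laboratory and method, and otherwise for screening only.

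If stored aliquots are batch-assayed instead, say that storage time will differ by visit. In a single run after the last draw, the baseline aliquot has been stored about 7 months longer than the month-7 sample (7 − 0), and the month-4 sample about 3 months longer (7 − 4). In either case, reconcile the 4°C statement in section 8 with the -80 °C statement in section 9.

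If samples have already been assayed, report laboratory and method by visit and carry the limitation into any statement about change from baseline.

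Cost: a few sentences of protocol text, plus either a possible change of follow-up laboratory or up to 18 extra assay sets. No extra visit or draw is needed, because the baseline-stage draw is already planned.

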- are HIV infected but are virologically suppressed (viral load <200 copies/mL);
- volunteer informed consent
- have medical clearance by a physician;
- expect to stay in Miami for the next 6 months; and

IRB Study Number: 20181032

Version 8, Date: 07/16/2021

- have documented risk of cardiometabolic disease.

Exclusion Criteria:

Individuals meeting any of the following criteria will not be eligible to participate in the study:

- have a diabetes diagnosis;
- at baseline meet criteria for current major depressive disorder or generalized anxiety disorder;
- meet criteria for current alcohol or other substance abuse disorders;
- have a lifetime history of bipolar disorder or other psychotic disorder;
- have a diagnosis of any neurodegenerative disorder or dementia (Parkinson's disease, Alzheimer's, vascular, frontotemporal dementia, etc.) or significant cognitive impairment as indicated by a Mini Mental Status Exam score <24;
- have contraindications to physical activity outlined in the American College of Sports Medicine standards; (g) have high suicide risk i.e., intent or plan to attempt suicide in the near future (a response of "yes" to questions 3, 4, and/or 5 on the Paykel Questionnaire);
- are unable to complete 10 m walk test;
- currently residing in a nursing or group home;
- have a terminal physical illness expected to result in the death within one year;

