We will use a multi-faceted recruitment strategy that has been successfully implemented at the University of Miami/Jackson Memorial Medical Center (UM/JMMC) Adult HIV Outpatient Clinic consisting of advertisements, informing clinic staff of the study, and direct recruitment by the CHW. The CHW (a UM employee who is to be determined) will coordinate with the Clinical Sciences Core and the Behavioral/Social Science & Community Outreach Core of the Miami Center for AIDS Research (CFAR). The CFAR Clinical Sciences Core (Core C) provides state-of-the-art facilities for implementation of clinical studies, clinical research and services including sample and data collection. The location of Core C next to the Special Immunology clinics allows recruiting participants in an efficient manner on the same day of clinic visit. Behavioral/ Social Science & Community Outreach Core (Core E) provides CFAR investigators with consultation and resources to expand behavioral clinical studies. HIV-infected patients receive

IRB Study Number: 20181032

Version 8, Date: 07/16/2021

primary care from their HIV care providers at the UM/JMMC Adult HIV Outpatient Clinic. The CHW will work with Clinic staff to educate them about the study as well as the inclusion/exclusion criteria. Clinic staff will identify potential participants through the electronic medical records and matched with the weekly clinic census. Clinic staff will introduce the CHW to potential participants during their regularly scheduled HIV care visit at the Clinic. The CHW will describe the study to the potential participant. If he is interested, then the CHW will go over the consent form. After the participant has signed the consent form, he will be asked to sign HIPAA Research Authorization – Form B, which authorizes study personnel to access the participant's protected health information, specifically the cardiometabolic parameters of interest, HIV/AIDS status, and viral load. No other individually identifiable health information will be shared with study investigators.

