As a pilot study, we will evaluate the feasibility of recruitment, assessment procedures, retention, acceptability, and implementation of HOLA in a sample of midlife and older Latinos living with HIV (**Aim 1**). Consistent with recommendations from biostatistical workgroups funded by NIH, this pilot study is not powered to test a hypothesis. This approach to analysis of feasibility data mirrors the structure of the first HOLA trial and other pilot trials conducted at the CNSA. Successful recruitment will be defined as meeting 100% of targeted sample (N = 18), with 20% or less of eligible subjects refusing to participate. Adequate retention will be defined as 85% or more of randomized subjects completing the post-intervention assessment. Acceptability is defined as 80% or more of sessions attended by subjects. To identify modifications needed in the design of a larger, confirmatory randomized controlled trial (**Aim 2**), we will use a project evaluation questionnaire developed by investigators at the CNSA and used in previous studies. The items are a mix of rating scales, yes/no questions, and open-ended questions that allow participants to give feedback in short answer format with specific interest in understanding the participants' opinions regarding the specific components of the intervention. To explore changes in cardiometabolic risk factors (waist circumference, dyslipidemia, hypertension, and glucose), psychosocial functioning (depression and anxiety severity, social support), and health-related quality of life (**Aim 3**), a one-way ANOVA will be used to illustrate the change in scores from baseline to post-intervention in all the outcome measures used.

A repeated measures ANOVA, as we have proposed, is appropriate to explore the intervention effects on cardiometabolic risk factors,

IRB Study Number: 20181032

Version 8, Date: 07/16/2021

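### The protocol does not say which medical-record value is the laboratory baseline, so a man's qualifying value may be reused and regression to the mean can appear as change in this single-arm study

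*Combined protocol and SAP*

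**What the plan says.** All of the following is in the combined protocol and SAP.

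- **Entry (section 5).** Men must "have documented risk of cardiometabolic disease". No marker, cut-off, source or look-back period is given. Men with a diabetes diagnosis are excluded.
- **Finding candidates (section 7).** "Clinic staff will identify potential participants through the electronic medical records and matched with the weekly clinic census". Advertisements and direct recruitment are also used, and section 8 opens by adding a consent-to-contact registry, which sits under the recruitment heading.
- **Baseline laboratory values (section 8).** "Prior to starting the baseline assessments, blood draws will take place at the UM/JMMC Adult HIV Outpatient Clinic". The next sentence reads: "Study staff will obtain initial HDL-C, LDL-C, triglycerides, insulin, and HbA1c levels via review of the electronic medical records". Neither sentence dates the record values, requires fasting, or says that they are the results of that draw.
- **Follow-up laboratory values (section 8).** "At 4 and 7 months after the initial interview, fasting blood samples will be drawn via venipuncture and stored at 4°C until analysis".
- **Allocation (section 8).** "After the baseline assessment, participants will be enrolled into the HOLA intervention". There is one arm.
- **Analysis (section 10).** Change from baseline is analysed by ANOVA, with a repeated-measures version described as suitable to "explore the intervention effects on cardiometabolic risk factors". The covariates are age, SES, years of education and medication changes.

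**The concern.** A single laboratory reading mixes a man's usual level with short-term variation. If he is chosen because a reading was out of range, a repeat reading lies closer to the average of the population he came from, even if nothing about him has changed. When the reading that got him into the study is also his baseline, that shift is counted as change during the study.

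The protocol leaves this open. Risk-based entry, a search of the record and a baseline read from the same record come together with no rule separating the qualifying value from the baseline value. No control arm would reveal the shift, and none of the listed covariates addresses it. Section 10 nevertheless describes the result in terms of intervention effects. Later investigators could then carry a selection artefact into their choice of outcomes or expected effects for the confirmatory trial.

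Measurement conditions raise a related problem. Follow-up samples are fasting, but no such condition is stated for the baseline record values. A systematic difference could follow, above all for triglycerides and for insulin and the HOMA index derived from it.

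**Working it through.** **Inputs from the documents.** N = 18, one arm. The retention target of 85% gives 0.85 × 18 = 15.3, so at least 16 completers. The protocol gives no alpha, effect size, SD or test-retest correlation, and says that the study is not powered to test a hypothesis. There is therefore no stated figure to reproduce.

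**Assumed inputs.** One normally distributed marker with SD 1. The correlation r between two readings in the same man is 0.6 to 0.9. Selection is from the upper half or upper third on the qualifying reading. HOLA has no effect. Significance is judged by a two-sided 5% paired t-test, which is a yardstick and not the protocol's analysis.

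**Formula.** If every man is selected above cut-off c on the marker and that reading is reused as baseline:

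expected fall = (1 − r) × φ(c) / (1 − Φ(c)), in SD units.

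- Upper half: c = 0, φ(c)/(1 − Φ(c)) = 0.399/0.5 = 0.80. The fall runs from 0.80 × 0.1 = 0.08 to 0.80 × 0.4 = 0.32 SD.
- Upper third: c = 0.43, 0.364/0.333 = 1.09. The fall runs from 1.09 × 0.1 = 0.11 to 1.09 × 0.4 = 0.44 SD.

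**Simulation with 18 men.** The table gives the share of trials showing a significant fall. With no bias, the rate in that one direction would be 2.5%.

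| Situation | r | Mean fall (SD) | Significant fall |
|---|---|---|---|
| All men, upper half, value reused | 0.9 | 0.08 | about 11% |
| | 0.7 | 0.24 | about 26% |
| | 0.6 | 0.32 | about 33% |
| All men, upper third, value reused | 0.9 | 0.11 | about 17% |
| | 0.7 | 0.33 | about 43% |
| | 0.6 | 0.44 | about 56% |
| One third of men, upper third, value reused | 0.8 | 0.07 | about 7% |
| Half of men, upper third, value reused | 0.7 | 0.16 | about 13% |
| All men, fresh draw after qualification | 0.6–0.9 | 0 | about 2.5% (5% two-sided) |

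The partial rows follow from scaling: 1.09 × 0.2 × 1/3 = 0.07 and 1.09 × 0.3 × 1/2 = 0.16. They treat the remaining men as unselected on that marker. With 16 completers, the range for the all-men rows is about 10% to 51%.

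**Direction.** These figures describe a marker selected for being high. Two markers differ.

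- *HDL-C:* if men qualified on a low value, the drift would be upward, which again looks like improvement.
- *HbA1c:* excluding diagnosed diabetes removes high values. As an approximation, suppose the top 10% to 30% of values are removed with no lower cut, and r is 0.9 to 0.5. The drift is then upward by (1 − r) × φ(c)/Φ(c): 0.1 × 0.195 = 0.02 SD at one end and 0.5 × 0.497 = 0.25 SD at the other. That looks like worsening. If instead the men lie between the 50th and 80th percentiles, the mean is (0.399 − 0.280)/0.3 = 0.40 SD, and the fall is 0.04 to 0.20 SD.

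**The case against.** The strongest reply is that the sentence immediately before the record-review sentence puts a clinic blood draw ahead of the baseline assessments. A natural reading is that the initial levels are the results of that draw, retrieved from the record. Being in the same record does not make two readings the same measurement. If that reading is right, and the draw does not itself decide eligibility, there is no bias from this source. This largely stands. The text permits reuse of the qualifying value but does not state it, so a reader who infers that regression to the mean will appear goes further than the documents allow. What remains is that the protocol neither links the two sentences nor says that the draw follows qualification.

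A second reply is that selection on lipids or HbA1c is itself assumed. The documented risk could be waist circumference or blood pressure, in which case a man's lipids may be hardly selected at all. This also stands, and it is why the partial-selection rows matter as much as the full-selection rows.

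Third, Aim 3 is exploratory, the primary aim is feasibility, and section 10 draws the design changes for the confirmatory trial from a project evaluation questionnaire. No passage says that Aim 3 changes will choose outcomes or set a sample size. That limits the consequence. It does not answer the point about bias, which a larger sample would not remove either.

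**Conclusion.** The point holds as an ambiguity that leaves room for bias; it is not a demonstrated bias. Nothing in the protocol prevents a qualifying value from serving as the laboratory baseline, and the single-arm change is described in causal terms.

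The size is conditional. It is 0.08 to 0.44 SD, with a significant improvement in about 11% to 56% of trials, only if every man qualified on that marker and the value was reused. It is 0.07 to 0.16 SD and about 7% to 13% if one third to one half did (upper third, r = 0.7 to 0.8). It is zero if a fresh post-qualification draw is the baseline. All of these rest on assumed correlations and cut-offs.

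Two further inferences should be resisted. One is that HbA1c must drift toward improvement: with diagnosed diabetes excluded, the direction is uncertain. The other is that the study's main conclusions are threatened: recruitment, retention and acceptability do not depend on these values. The point is worth settling because the remedy is cheap and works whichever marker qualified a man.

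**What to change.** **Section 8.** Define the Aim 3 laboratory baseline as the already planned clinic draw before the baseline assessments, taken after eligibility is settled and under the same fasting condition as follow-up. State that the value that documented a man's risk is never used as his baseline. Record the date and source of each baseline value. Flag any man for whom only the qualifying value exists, and repeat the analysis without him.

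**Section 10.** Replace the reference to intervention effects with changes during HOLA, and state that uncontrolled change cannot be attributed to HOLA.

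Do not present the shift from qualifying value to baseline as a comparison period without HOLA. That shift carries the selection effect, whereas change from a fresh baseline does not, so setting them side by side would bias the reading against HOLA.

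**Cost.** Protocol wording, a date and source for each value, and a fasting requirement on a draw that is already planned. A few record values may prove unusable, and the conclusion that Aim 3 can state is weaker.
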